5.2 Randomisation

After obtaining oral and written informed consent, subjects meeting the eligibility criteria were randomized to one of the treatment groups in a 1:1 ratio. The randomization schedule was generated using a computer program and verified for accuracy using strict quality control procedures. Eligible patients received a masked treatment assignment with a unique randomization code based on the randomization list. The assigned randomization code was captured in the electronic Case Report Form (eCRF). This randomization code was designed as not to disclose any treatment assignment, see section 5.1 of the protocol.

Until the moment of unmasking, the treatment assignments linked to the codes should only be accessible for the individuals appointed by the Sponsor as Qualified Persons responsible for Pharmacovigilance. Emergency Unmasking should only be done if knowledge of treatment assignment was considered relevant for medical care of the patient. The randomization code will be broken when all subjects have finished the study at the formal request from the study statistician after the Clean file report has been signed, any early unblinding has been accounted for and the database has been locked.

6 Assessments

6.1 Primary efficacy endpoint criteria for assessing clinical resolution

A subject will be considered cured if resolution of all the following clinical signs are observed, resulting from a slit lamp examination:

- No corneal inflammation (including subepithelial infiltrates, stromal infiltrates and oedema) that
 requires treatment, with a healed corneal epithelium and minimal punctate staining (10 dots or less
 equivalent to Grade 1 on the Oxford Scale).
- No or mild conjunctival inflammation (including bulbar injection, bulbar oedema, tarsal hyperemia): mild conjunctival inflammation is acceptable if related to other concurrent conditions such as blepharitis.
- No limbitis, scleritis or anterior chamber inflammation.
- No relapse within 30 days of discontinuing all topical and systemic therapy given for Acanthamoeba keratitis.

For regulatory and verification reasons, there is an additional 60-day follow-up to exclude late relapses.

Relapse of infection is identified by a positive culture, unfortunately very insensitive due to the persistence of deep organisms, supported by an increase in cysts on confocal (also insensitive in severe disease) or using clinical criteria: development of more severe corneal inflammation, melting, ulceration hypopyon, development of ring abscess necessitating another intensive course of therapy.

The primary hypothesis to be tested is that the CRR_12 of subjects treated with 0.08% PHMB monotherapy, is superior, or worse by no more than an acceptable pre-defined 0.20 non-inferiority margin (Δ), compared to the CRR_12 of 0.02% PHMB + 0.1% propamidine combination therapy, administered according to the Treatment and Follow-up Protocol presented on page 16 of the Protocol.

6.2 Secondary efficacy endpoints assessment

6.2.1 Assessment of BCVA

BCVA is being determined using pinhole with or without spectacles, soft contact lenses or rigid contact lenses. Detailed information about the procedure is provided in the Study Operation Manual. International Council of Ophthalmology approved a Visual Acuity Measurement Standard (VAMS) in 1984 (3). In Table II in the VAMS different types of notations of visual acuity are presented, one being the Snellen notation, such as 20/16 when measured in feet or 6/4.8 when measured in metres. Other notations are the decimal notation, 20 divided by 16 (6 divided by 4.8) which equals 1.25, the visual angle (the inverse of the decimal notation, 0.80) or the logarithm (base 10) of the visual angle, referred to as LogMAR.

LINK Medical Study ID: PSR012

In addition, refraction will be assessed, together with any potential relationship between BCVA and refraction.

6.2.2 Assessment of corneal scarring

Corneal scarring is being assessed as *Present* or *Absent*, using the slit lamp biomicroscopy performed by the examining ophthalmologist. Detailed information about the procedure is provided in the Study Operation Manual.

6.2.3 Assessment of ulceration severity

Ulceration severity is being assessed as *Present* or *Absent* by the examining ophthalmologist using the slit lamp biomicroscope.

6.2.4 Pupil test

Pupil test (swinging light test) is reported as Normal; Abnormal, NCS; Abnormal CS. The specific abnormalities will be listed.

6.2.5 Assessment of anterior chamber inflammation

Anterior chamber inflammation is being assessed using a 3-grade scoring procedure using the slit lamp biomicroscope: Abnormal Clinically significant (CS), Abnormal Not CS (NCS), and Normal. Clinically significant events are defined as "any variation, symptoms, or testing that has medical relevance according to the investigator and may result in an alteration in in medical care".

6.2.6 EQ-5D-5L and VFQ25 assessments

EQ-5D-5L and VFQ5 are two instruments for subject-reported outcomes; the former addressing the overall health status of the subjects and the latter their visual function status. More detailed information can be seen in appendices 2 and 3 of the protocol.

6.3 Secondary safety endpoints assessment

6.3.1 AEs

Recording of AEs will commence with signing of the ICF. AEs will be captured in the CRF. AEs will be followed up by the investigator as specified in section 8 of the protocol, AE Reporting. Standard CDISC STDM annotation is being used for AE data.

6.3.2 Clinical laboratory tests assessment

Clinical laboratory results (haematology, biochemistry and urinalysis) were conducted at the Screening or Baseline visit and at the End-of-study visit. These are annotated using standard SDTM names. Clinical laboratory tests will be presented with summary statistics. In addition, the tests will be analysed with ANCOVA (baseline value of respective laboratory test and treatment group will be included in the model). All results will be regarded as descriptive only. The p-values will be used to flag safety and tolerability variables worthy of further attention.

7 Methods of Analysis

7.1 General

All statistical analyses will be performed in accordance with the ICH E9 guideline for Statistical Principles for Clinical Trials (1), using SAS® (Version 9.4 or higher, SAS Institute Inc., Cary, NC, USA).

7.1.1 Presentation of Results

All results will be presented for each visit by treatment group and in total, unless stated otherwise. It should be clearly stated which unit applies to each presented variable.

Continuous data will be summarised using descriptive statistics, and the following parameters will be reported:

- number of subjects with evaluable observations and missing observations
- arithmetic mean and change from baseline with standard deviations

LINK Medical Study ID: PSR012

- median
- first and third quartiles
- minimum and maximum

Categorical data will be presented using absolute frequency and percentage. When the absolute frequency is zero, the percentage will not be presented. Unless stated otherwise, the denominator for percentage calculations will be the total number of subjects in the applicable analysis set, including subjects with missing data. For variables with missing values, the number and percentage of subjects with missing values will be presented.

Significance tests will be two-sided and performed at the 5% significance level, unless stated otherwise. When reporting the results of significance tests, p-values will be presented.

All confidence intervals (CIs) presented will be two-sided with a nominal confidence level of 95%, unless stated otherwise.

Data will be presented using an appropriate number of decimal places, to ensure that undue precision is not implied (e.g. the number of decimals should not exceed the accuracy of the measuring instrument). Raw data will be presented with the same number of decimals as collected, and derived data with an appropriate number of decimals based on general practice, mathematical rationale or scientific rationale.

Minimum and maximum values will be presented with the same number of decimals as the analysed variable and the other descriptive statistics will be presented with one decimal more. Percentages and proportions will be presented with one decimal. Odds ratios and hazard ratios will be presented with 3 decimals, and small and large values will be presented as '<0.001' and '>999.999' respectively. CI bounds will be presented with the same number of decimals as the corresponding point estimate, and p-values will be presented with 4 decimals or as '<0.001'.

Mock tables and graphs are presented in the Data Display Plan (DDP), which is a supplementary document to this analysis plan. Individual subject data listings will be presented according to the ICH E3 guideline for Structure and Content of Clinical Study Reports (2), unless stated otherwise.

7.1.2 Baseline

Unless stated otherwise, the baseline value for a parameter is defined as the last non-missing value before the first dose of the investigational medicinal product (IMP).

7.1.3 Analysis Relative Day

The analysis relative day for an assessment/value is defined as the time in days from the date of randomization to the date of the assessment. The date of randomization is considered as day 1, and earlier dates will correspond to a negative day. In the Schedules of assessments table on page 22 and 23 of the protocol, the day of randomisation, which also encompass some baseline measurements and drug dispensing, is called Day 0. As CDISC does not use 0 for day numbering, Day 1 will be used for the day of randomisation. Hence, the day numbering after the baseline day in the Schedules table will be increased by one.

7.1.4 Analysis Visit

An analysis visit is defined as a categorical variable used to classify values within an analysis variable into temporal or conceptual groups used for analyses.

The visits as defined in the case report form, CRF, will be used as analysis visits. The Schedule of Assessments table provide acceptable deviations from the specified study day at which study visits should occur. These are \pm 2 days up to study day 22, called study day 21 in the Schedules table, ref. section 7.1.3 above, \pm 3 days from study day 31 to 30 days after end of treatment (EoT), and \pm 5 days at the 90 day after end of treatment visit. A review of assessment times will be conducted before the clean file meeting. Necessary revisions will be documented in the Clean file report. Results tables will present statistics by visit number. Where deemed necessary, longitudinal analyses will use the observed durations from baseline. The mean duration in days between visits will be presented.

Study day windows

Study visit day	Target study day of visit	Window of study day visit
0	0	± 0 days
7	7	± 2 days
14	14	± 2 days
21	21	± 2 days
30	30	± 3 days
60	60	± 3 days
30 days after previous visit§ until resolution	30 after previous visit	± 5 days
30 days after EoT	30 days after EoT	± 3 days
90 days after EoT	90 days after EoT	± 5 days

[§] The protocol states "and every 30 ± 5 days until resolution". This is interpreted as 30 days after the previous visit, and not a multiplicity of 30 days based on a fixed setup from baseline, i.e. not 31+60+n*30.

In general, data from unscheduled visits will be presented in data listings only and not included in analysis or summary tables. An exception to this is data used to confirm eligibility in association with screening or randomisation where the last assessment will be considered in summaries of screening data.

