- 3. If within 90 days after end-of-treatment and within 11 months (Day 335) after randomization the subject relapses, and cultures are negative for *Acanthamoeba*, treatment with the study drug will be re-started according to the treatment schedule, starting with the Day 0 treatment regime. Assessments and visits will also be restarted at Day 0, Day 30 and all consecutive visits of the treatment phase. A detailed treatment plan and follow-up protocol is provided in Section 5.3.
- 4. End-of-study is defined as: (a) the last follow-up visit at 90 days after end of treatment, (b) the day of study drug unmasking in the event of the subject becoming a Treatment failure, (c) if withdrawn from the trial of other reasons, (d) if a subject has been treated for 12 months after randomization (also a Treatment failure).
- 5. Screening and baseline assessments will take place on Day -2 to 0, before randomization and study drug administration.
- 6. For subjects who have not reached the age of majority (i.e. 18 years of age in most jurisdictions), the subject must provide assent (written or verbal) and the parent/guardian/legally authorized representative must provide written informed consent before the subject's participation in the study.
- 7. All medical and medication history related to the current eye infection will be reported. For the remaining medical and medication history, only the last 30 days before signing the ICF will be reported in the case report form (CRF).
- 8. Confocal microscopy is optional if already performed within 7 days prior to study entry as part of standard care providing the images are available to the Investigator to assess.

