DISCONTINUE TREATMENT (includes topical steroids, oral NSAIDs and topical antiamoebics/microbials) is when any ulcers have healed and all signs of *Acanthamoeba* keratitis related inflammation have resolved (see detailed description in the protocol; mild conjunctival inflammation related to drugs or other condition such as blepharitis are acceptable) at or before 12 months (365 days) from study entry. Clinical resolution (CR) after 365 days is a failure (see Box XVI - RELAPSE AFTER 11 MONTHS). It is recommended that topical steroids are discontinued 2-4 weeks before discontinuing topical anti-amoebics.

BOX V Follow-up visit (Day 30 after last treatment)

Deterioration of inflammation: Patients in this subset may deteriorate due to: XI Relapse of Infection or XII Exacerbation of inflammation in which case they are managed as described in paragraph II a, b for these issues.

BOX VI Follow-up visit (Day 90 after last treatment)

Follow-up visit 90 days (D90) after last treatment has two outcomes: if there are no signs of a relapse by 15 months (Day 455) at latest, the pathway goes to Box **VII** - TREATMENT SUCCESS maintained STUDY-END-POINT. In the event of signs of a RELAPSE, the pathway is the same as for relapses in box XI or XIIP).

BOX VII Treatment success maintained study end point. **EXIT TRIAL**

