7.9.1 Primary Efficacy Variable

The main endpoint disease resolution 12 months after baseline will be assessed at each visit up to study day 365.

Clinical resolution 12 months after baseline for a patient is defined as:

The percentage of subjects cured 30 days after discontinuing all study therapies, within 12 months of randomization. A clinical resolution classification requires a Yes response to the eCRF variable CRYN question: "Was clinical resolution obtained?" at one of the study visits from day 1 up to study day 365 in combination with a response *No* to the eCRF variable RELAPYN question "Did the subject experience relapse since the last visit?" at the pursuing visits, up to the last recording of this information. There should be no relapses after (the last) clinical resolution classification. Discontinued subjects will be regarded as not cured.

For patients defined as fulfilling disease resolution within 12 months, the date of the visit at which annotated CRYN is first answered with a Yes will be used as the date of resolution. The time-to-cure secondary variable will be the number of days from randomisation to the visit where resolution was recorded.

Since it is also possible to test for non-inferiority if the superiority hypothesis is not met, additional conditions are specified (see list below) to meet the strict requirements of a non-inferiority study, making it feasible to test for non-inferiority using the results from the superiority analysis, without a further separate analysis. The 90% CI for the difference between the treatments obtained from the superiority analysis gives the necessary information. Position of the lower end of the CI relative to a pre-defined agreed 0.20 non-inferiority margin (Δ) provides the key information for making decisions (conclusions) about non-inferiority.

PHMB has received the orphan drug designation. The use of 90% CI for the difference between the two treatments is to provide a 95% lower CI limit for non-inferiority.

The additional conditions specified to make testing for non-inferiority feasible are the following:

- Pre-defined non-inferiority margin (Δ =0.20) based on both clinical and statistical considerations, i.e., chosen on the basis of external information and not chosen to fit the data.
- Analysis of the FAS and the PPAS, giving similar results with respect to p-values and CIs for the
 efficacy measure at issue.

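### The SAP's day-365 limit for clinical resolution ends one day before the protocol's, and the 12-month visit has no window and no stated role in the primary endpoint

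*SAP*

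**What the plan says.** **The limit in the protocol.** Randomization is on Day 0 in the Schedule of Assessments. Section 5.3.1, Box IV, accepts resolution "at or before 12 months (365 days) from study entry" and adds: "Clinical resolution (CR) after 365 days is a failure".

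**The limit in the SAP.** Section 7.1.3 changes the origin: "As CDISC does not use 0 for day numbering, Day 1 will be used for the day of randomisation". It continues: "Hence, the day numbering after the baseline day in the Schedules table will be increased by one". Section 7.9.1 then requires a Yes to the clinical resolution item (CRYN) "at one of the study visits from day 1 up to study day 365".

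**The visits.** The protocol has visits at Day 60 ± 3 and then every 30 ± 5 days until resolution. On the 30-day interval, the footnote to the window table in SAP 7.1.4 says: "This is interpreted as 30 days after the previous visit, and not a multiplicity of 30 days based on a fixed setup from baseline". That table has no 12-month row. After the rolling visit it lists only the visits 30 and 90 days after end of treatment. Section 7.1.4 also sends unscheduled visits, in general, to listings only.

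**The 12-month visit.** Footnote 4(d) of the Schedule triggers the End-of-study visit, which includes a slit lamp examination, once a subject has had 12 months of treatment since randomization. It gives no day number or window and labels that subject a treatment failure.

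**The concern.** CRR_12 is the primary variable, and its time limit decides success or failure for anyone who resolves near month 12. Two documents that differ by a day allow two programmers to derive different primary outcomes from the same record. The SAP is not consistent within itself either: the text of 7.1.4 uses the new numbering (day 22 for the Schedule's Day 21), while the window table below it keeps 0, 7, 14, 21, 30 and 60.

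The second part concerns detection. Resolution counts only when recorded at a study visit. If the last countable visit can fall weeks before the limit, and the 12-month examination has no stated role, a subject who resolves in between may be counted as not cured for reasons of scheduling. This lowers the recorded CRR_12, which also feeds the non-inferiority comparison and the condition that the control shows its expected efficacy. With 65 subjects per arm, one subject is 1/65 = 1.5 percentage points.

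**Working it through.** **1. The protocol's own day count.** 335 + 30 = 365 and 365 + 90 = 455. These match its 11-, 12- and 15-month limits, so Day 365 is deliberate and is counted from Day 0.

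**2. The SAP limit in elapsed days.** Under 7.1.3, for visits on or after randomization:

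- analysis day = (visit date − randomization date) + 1
- analysis day 365 is 364 elapsed days
- the protocol limit of 365 elapsed days is analysis day 366

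The 7.9.1 phrase starts at day 1, and SAP 8.5 also adds one day to the time from randomization to resolution. Both fit this reading. A visit exactly on protocol Day 365, including a 12-month End-of-study visit held that day, is inside the protocol limit and outside the SAP limit.

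**3. Where the last countable visit can fall.** All of these schedules are in window:

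| Schedule | Last visit by Day 365 | Next visit |
|---|---|---|
| Day 60, then every 30 days | 60 + 10 × 30 = 360 | 390 |
| Day 60, then every 31 days | 60 + 9 × 31 = 339 | 370 |
| Day 63, then every 35 days | 63 + 8 × 35 = 343 | 378 |

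**4. Simulated visit timing.** Inputs: Day 60 ± 3, then 30 ± 5 from the preceding visit, or a fixed grid of 60 + 30k ± 5. Assumption: whole-day deviations uniform over each window; 400,000 schedules. Results describe subjects still on monthly visits at month 12:

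| | Rolling | Fixed grid |
|---|---|---|
| Mean gap from last visit to Day 365 | 14.0 days | 5.0 days |
| Maximum gap | 34 days | 10 days |
| Gap over 10 days | 58% | 0% |
| Visit exactly on Day 365 | 3.7% | 9.1% |

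With rolling visits, the visit nominally due on Day 360 falls after Day 365 in 30%.

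**5. From visit timing to lost resolutions.** The documents do not say how many subjects resolve late. Assume a constant hazard h and true 12-month rates p of 63% (the protocol's adjusted control rate) and 83% (that plus the planned 0.20).

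- h = −ln(1 − p)/365, which is 0.00272 per day for 63% and 0.00485 for 83%
- share of the arm resolving in the last g days = (1 − p) × (exp(h × g) − 1)
- rolling, g = 14: 0.37 × (exp(0.0381) − 1) = 1.4 points; 0.17 × (exp(0.0680) − 1) = 1.2 points
- fixed grid, g = 5: 0.5 and 0.4 points

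Averaging over the simulated gaps, rather than using the mean gap, gives the same rounded values. The rolling loss is 0.014 × 65 = 0.9 subject in the control arm and 0.012 × 65 = 0.8 in the test arm, and it moves the difference by about 0.2 points. Ending the limit at 364 days adds about 0.1 point per arm.

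**6. Effect on power.** With 58 evaluable per arm, 83% against 63%, and two-sided alpha 0.10, power is 78.9%. It is 78.0% if 1 point is lost in both arms and 75.2% if 5 points are lost.

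**The case against.** **The shift may not be intended.** Section 7.1.3 renumbers the Schedule days, 365 is not a Schedule day, and the 7.1.4 table keeps Day 0 numbering. That is fair, and the statistician may mean 365 elapsed days. But 7.1.3 defines the relative day for assessments generally, the text of 7.1.4 follows it, and 7.9.1 starts at day 1. The literal reading is the natural one, and the limit needs a single meaning.

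**A reader might infer that no visit is tied to Day 365.** The documents do not support that. Footnote 4(d) provides a 12-month End-of-study visit with a slit lamp examination, and Box XVI classifies status at day 365. What is missing is a window and a statement that a resolution recorded there counts.

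**A reader might also infer that resolutions by Day 365 are generally scored as failures, or that the 30% and 58% are misclassification rates.** Neither follows. Only subjects who first resolve after their last countable visit, or who are seen exactly on Day 365, can be affected. The percentages describe visit dates. Nor is failure certain for a resolution recorded just after Day 365: SAP 7.2.1 uses the last disease status in the FAS with no time limit, while 7.2.2 limits the PPAS to 12 months. That conflict with 7.9.1 is one more reason to settle the limit.

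**Any endpoint read at periodic visits has a detection gap, and the SAP footnote only interprets an ambiguous protocol phrase.** This stands. The SAP, dated July 2021, describes randomization in the past tense and cannot re-time visits already held. A fixed ± 5-day grid would also widen the allowed interval from 25–35 to 20–40 days. The review of assessment times before the clean file meeting helps, but it does not state the limit.

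**Conclusion.** The mismatch in the limit holds: read with its own day convention, SAP 7.9.1 closes the window one day before the protocol does, and the SAP mixes two conventions. Its direct reach is narrow, about 4% of subjects still on monthly visits, and only those first recorded as resolved on that day change status.

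The wider gap comes from rolling visits together with a 12-month visit that has no window and presumes failure. It is worth about 1.2 to 1.4 points of CRR_12 per arm and about 0.2 points of the difference, small against a 0.20 margin. These figures rest on uniform in-window deviations, a constant hazard and true rates of 63% and 83%. A different late hazard would change them. The same rule applies in both arms, but the loss need not be equal if time to cure differs, as the protocol hypothesizes. The sample size calculation is not in question here. The correction is worth making because it is nearly free and can change an individual primary outcome.

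**What to change.** 1. In SAP 7.9.1, define the limit as visit date minus randomization date of at most 365 days (analysis day 366).
2. Use one day convention in SAP 7.1.3, in the text and table of 7.1.4, and in 7.9.1.
3. State in the SAP that CRYN at the 12-month End-of-study visit counts when that visit is on or before the limit, and reconcile this with the failure label in Schedule footnote 4(d).
4. Add a sensitivity analysis of CRR_12 that accepts a resolution first recorded at the next visit after Day 365, where one was held.
5. An anchored visit in Days 355 to 365 would shorten the gap, but only for subjects not yet past that point. It is optional.

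Items 1 to 4 cost a few SAP sentences, one added analysis of data already collected, and a clarification of one Schedule footnote. The SAP changes should be made before the code is broken. Item 5 would need a schedule change.

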3.1.3. Treatment Period

On Day 0, subjects will arrive at the clinical research center for the baseline assessments and will receive instructions on how to apply the eye drops. Subjects will be randomized to 1 of the 2 treatment groups.

Subjects will receive multiple doses of 0.08% PHMB + placebo or 0.02% PHMB + 0.1% propamidine combination therapy in the affected eye until resolution according to the treatment schedule presented in Section 5.2 Drug dosage and Administration.

On Day 0, the first application of study medication will be done at the research center after completion of all baseline assessments and randomization. Thereafter, subjects will leave the clinical research center and study drug will be self-administered at home. Subjects will return to the clinical research center for ambulant visits on Days 7, 14, 21, 30 and every 30 days until resolution.

Assessments will be performed during the treatment period as presented in the schedule of assessments.

Follow-up medical examinations will be performed 30 and 90 days after end of treatment. The specific procedures that will be performed are presented in the schedule of assessments.

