7.4.1.1.2. Justification on Clinical grounds

The Sponsor proposes as clinically acceptable a non-inferiority margin of 0.20: this is within the accepted level for a study of this kind in view of the following:

- A poor response to therapy is common in this disease. Disease progression is slow in this disease (over weeks and months) and clinicians have to assess the effect of treatments every 1-2 weeks, in cases not progressing well, and modify therapies to optimize outcomes. Because of the disease chronicity the use of an ineffective treatment for these periods results in a delayed response, but no serious short term morbidity. The study results may indicate non-inferiority, when at worst the true difference in proportion 'cured' (Combined PHMB alone) is 0.20. The most likely impact of such a finding on clinical practice will be to encourage the use of PHMB monotherapy as a first line treatment.
- However, if PHMB monotherapy fails in clinical practice during the early stages of treatment, which is to be expected in some subjects, the clinician is unlikely to abandon the good clinical practice of monitoring the disease progress closely, and adding other antiamoebics to the therapy when necessary.
- At worst, the impact of the study finding might result in a little delay (matter of days) in starting a combined treatment in some patients, whilst giving a chance for the biguanide mono-therapy to act. This scenario is unlikely to result in blindness or serious morbidity. It may cause some delay in the clinical resolution.

• By contrast, the possibility that the true difference may be much smaller than 0.2, or even in favor of PHMB mono-therapy, will have important beneficial consequences for patients and ophthalmic services.

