7.10.7 Worsening of corneal inflammation

This is defined as development of ring abscess and/or hypopyon despite >30 days of treatment with the study drug. The table is presented in the DDP.

Rate of subjects with a relapse 7.10.8

The rate of subjects with relapse will be tabulated, see the DDP. Relapse is recorded in the annotated variable RELAPSYN.

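### SAP 7.1.4 writes no post-baseline exception to its listings-only rule for unscheduled visits, so event-type findings seen only between monthly visits can be left out of the tables

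*SAP*

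**What the plan says.** The rule in SAP 7.1.4, which opens with the qualifier in general, is that "data from unscheduled visits will be presented in data listings only and not included in analysis or summary tables". It continues: "An exception to this is data used to confirm eligibility in association with screening or randomisation". No exception is written for post-baseline efficacy or safety findings. SAP 7.10.3 treats unplanned laboratory samples in a similar way: they are listed, and commented on if thought necessary.

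Protocol 3.1.3 sets treatment-period visits on "Days 7, 14, 21, 30 and every 30 days until resolution". The window table in SAP 7.1.4 allows ±5 days on the repeating 30-day interval.

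SAP 7.10.7 defines worsening of corneal inflammation as "development of ring abscess and/or hypopyon despite >30 days of treatment with the study drug" and refers to the Data Display Plan for the table. For the primary variable, SAP 7.9.1 states: "The main endpoint disease resolution 12 months after baseline will be assessed at each visit up to study day 365". SAP 7.10.5 describes intraocular pressure as a value in mmHg taken at all visits.

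**The concern.** Leaving unscheduled records out of means by visit is ordinary practice. It works differently for a variable that counts a subject once if a sign ever appeared, because one record can change the subject's classification. The worsening variable covers only the period after 30 days of treatment, which is when visits become monthly. If a subject attends between visits because the eye is worse, and the sign has gone by the next planned visit, the database holds the finding but a table built from scheduled visit forms does not.

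What is at stake is mainly the completeness of one secondary safety rate and of the pressure summary. There is a narrower ambiguity in the dating of clinical resolution and in relapse after it.

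**Working it through.** The plan states no figure for this, so the check is mainly a comparison of passages, followed by an illustration.

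**1. Is there a post-baseline exception?** None is written. The words at the start of the rule leave room for discretion but name no variable that escapes it.

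**2. Do the documents create occasions for off-schedule findings?** Yes, in three places.
- Protocol 5.3.2 (Box VIII) has poor response judged three weeks after trial entry or after a restart, and its criteria include ring abscess and hypopyon. Footnote 3 to the Schedule of Assessments, on relapse after end of treatment, resumes visits at Day 0, then Day 30 and onward. The three-week assessment after such a restart therefore has no planned visit. It bears on the worsening variable only if the 30 days are cumulated over treatment courses, which the SAP does not say.
- Protocol 5.3.1 (Box II) says deterioration can occur at any stage of treatment and asks the investigator to separate relapse from exacerbation. Exacerbation during treatment has no visit column of its own.
- Protocol 6.1.6 calls for ophthalmoscopy outside the schedule when vision worsens or when the pupil test or pressure is abnormal.

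**3. Which counts depend on visit forms?**

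| Variable | Source in the documents | Exposed? |
|---|---|---|
| Adverse events | Recorded whenever observed or reported (Protocol 8.2); frequency tables not by visit (SAP 7.10.2) | Not in this way |
| Secondary complications, including secondary glaucoma | Adverse event data (SAP 7.10.12) | Not in this way |
| Surgery, non-study therapy | Medication/therapy variable (SAP 7.10.9, 7.10.10) | Not in this way |
| Ring abscess, hypopyon | No source named (SAP 7.10.7); ring abscess is listed under the slit lamp examination (SAP 7.9.3) | Yes, if built from scheduled forms |
| Intraocular pressure | Value at each visit (SAP 7.10.5) | Peak values only |
| Clinical resolution | A Yes at a study visit up to day 365 (SAP 7.9.1) | Possibly; not stated whether unscheduled visits count |
| Relapse | Question covering the time from the previous visit (SAP 7.9.1) | Partly |

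On resolution, a Yes first given at an unscheduled visit would, under the general rule, be dated from the next scheduled visit, up to about one interval (25 to 35 days) later. It could be lost if it fell close to day 365. On relapse, if the event is recorded at an extra visit, a later scheduled answer of No can be correct for its own interval while the earlier Yes is excluded.

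**4. Illustration.** For a finding lasting D days, with onset at random between visits G days apart, the chance that a scheduled visit sees it is min(1, D/G). G follows from 30 ± 5 days. D is assumed, because neither document gives a duration.

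| D (days) | G = 25 | G = 30 | G = 35 |
|---|---|---|---|
| 3 | 12% | 10% | 9% |
| 7 | 28% | 23% | 20% |
| 14 | 56% | 47% | 40% |
| 21 | 84% | 70% | 60% |
| 30 | 100% | 100% | 86% |

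Example: 14/30 = 0.47, so 1 − 0.47 = 0.53 are not seen at a scheduled visit. That 53% is an upper bound on the loss caused by the rule. It includes episodes that nobody saw, and it ignores relapse visits, End-of-study visits and adverse event records.

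**The case against.** A reader might infer that the SAP discards all unscheduled data, and that worsening and pressure events are therefore under-counted, most in the arm with more poor responders. The documents do not support that reading, for five reasons.

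- The rule is qualified as general, and the visits defined in the case report form serve as analysis visits, with assessment times reviewed before the clean file meeting. The form is not available here, so which visits would count as unscheduled cannot be checked.
- The Relapse and End-of-study columns of the Schedule include slit lamp and pressure. End-of-study covers the day of unmasking for treatment failure, and Protocol 4.4 asks for these assessments at discontinuation where possible.
- The remark that "clinicians have to assess the effect of treatments every 1-2 weeks, in cases not progressing well" comes from the clinical case for the non-inferiority margin (Protocol 7.4.1.1.2). It describes practice and sets no study visit. The same section calls progression slow, over weeks to months, and long-lasting signs would mostly be seen at monthly visits.
- The SAP defines no pressure event or threshold, so there is no such event to under-count.
- The Data Display Plan, which holds the worsening table, is not available, so its data source is unknown.

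These points limit the concern but do not remove it. Ring abscess and hypopyon are also entry findings (Protocol 4.1), and under Protocol 8.1.3 a pre-existing sign becomes an adverse event only on recurrence after recovery or on a clinically significant exacerbation, so the adverse event route is not certain to catch them. Protocol 5.3.2 (Box IX) expects most poor responders to improve on anti-inflammatory treatment, so many episodes will not end in an exit visit.

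A further objection is that counting every record gives closely watched subjects more chances of an extreme value. That is true and should be made visible.

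**Conclusion.** The concern holds as a risk of under-counting written into the plan, not as a shown under-count. Followed as written, SAP 7.1.4 can leave out of the tables a ring abscess, a hypopyon or a peak pressure seen only at an unscheduled visit, and it leaves unclear whether a resolution or relapse recorded only there counts.

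The size is unknown. It depends on how long findings last, how many unscheduled visits occur, and what source the worsening table uses. The upper bound is about half for findings assumed to last two weeks, and close to nothing for findings lasting a month or more. The direction between arms is also unknown. For CRR_12 the exposure is narrow: a lasting resolution would normally still be present at the next scheduled visit, which leaves mainly resolutions first recorded close to day 365 and relapses recorded only at an extra visit. This is a worthwhile, inexpensive correction; it does not put the primary conclusion in doubt.

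**What to change.** Add to SAP 7.1.4, before the code is broken: event-type variables (clinical resolution, relapse, ring abscess, hypopyon) and maximum post-baseline intraocular pressure use all post-baseline records up to the cut-off for that variable, scheduled or not; by-visit summaries use scheduled visits only. Name the source variables for the worsening table in SAP 7.10.7. Report the number of unscheduled visits by arm, so that any difference in the chance of detection can be seen.

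The three-week assessment after a restart (Protocol 5.3.2) and the restarted visit schedule (footnote 3 to the Schedule of Assessments) also need to be reconciled.

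The cost is one SAP sentence, a small programming change and one extra table. No new data are needed. The downside is that subjects seen more often have slightly more chances of a recorded event.
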